#### 12.1.3 BIOMICROSCOPY

An external magnification and biomicroscopy will be performed using a slit-lamp. Magnification will be consistent with standard clinical practice. The subject will be seated. Examinations of the conjunctiva (hyperemia and edema), cornea (staining, stromal edema, and epithelial edema), anterior chamber (cells and flare), eyelid (erythema and edema), iris/pupil, and lens (lens status and lens opacity for phakic only) will be performed at all scheduled visits for both eyes. The result scoring values are None (0), Mild (+1), Moderate (+2), Severe (+3), and Hypopyon (+4 for anterior chamber cells only). Positive findings will be graded as being clinically significant (CS) and being non-clinically significant (NCS). A "No positive findings" result as collected on the CRF is considered a score value of 0 and NCS. Resolution of corneal edema (a grade of 0 for both stromal edema and epithelial edema) and resolution of epithelial edema (a grade of 0 for epithelial edema) will be identified and analyzed for efficacy.

#### 12.1.4 TOMOGRAPHY (PENTACAM®, SELECTED SITES ONLY)

Tomography assessments using a Pentacam® will be performed at selected sites only for both eyes at all scheduled visits. Measurements of CCT, superior corneal thickness (SCT), temporal corneal thickness (TCT), nasal corneal thickness (NCT), and inferior corneal thickness (ICT) will be collected and analyzed for efficacy.

### 12.1.5 V-FUCHS QUESTIONNAIRE

Patient-reported V-FUCHS questionnaire will be administered at the Baseline, Week 4, and Week 8 visits (Wacker 2018). Raw questionnaire data will be processed and be converted to Rasch-based scores including visual acuity factor mean score and SD and glare and diurnal variation (Glare Factor) mean score and SD. Rasch-based factor mean score will be analyzed for efficacy.

## 12.2 Primary Efficacy Analysis

The primary comparisons in this trial will be within a treatment group on the mean change from baseline CCT by ultrasound pachymetry at Week 4/Day 28 (visit 4) for each of netarsudil QD and BID. The summary will be provided for the study eye. The primary efficacy endpoint change from baseline in CCT will be summarized using continuous descriptive statistics and analyzed primarily using one-sample t-tests by treatment group; comparisons between treatment groups (QD – BID) will be completed using two-sample t-tests. Sensitivity analyses will be completed using Wilcoxon signed-rank tests within a treatment group, Wilcoxon rank sum tests between treatment groups and an analysis of covariance (ANCOVA) model with terms for baseline CCT value and treatment.

The mean change from baseline in CCT for each treatment group along with 2-sided p-values and 90% and 95% CIs around the change from baseline within each treatment group for the mean from one-sample t-test will be presented. The mean difference in change from baseline between treatment groups along with 2-sided p-values and 90% and 95% CIs for the mean differences between treatment groups from two-sample t-test will be presented. P-values from Wilcoxon signed-rank test within each treatment group, and Wilcoxon rank-sum test between treatment groups will be presented. The least squares (LS) mean for each treatment group along with 2-sided p-values and 2-sided 90% and 95% CIs around the change from baseline within each treatment group will be presented from the ANCOVA model.

Comparisons between treatment groups on the change from baseline in CCT will also be made including the LS mean difference and the corresponding 2-sided p-values and 90% and 95% CIs.

Example SAS® code for the primary efficacy analysis on change from baseline (CHG\_CCT):

#### One-sample t-test within a treatment:

```
proc ttest data = indata;
  var CHG_CCT;
  by treatment;
run;
```

#### Wilcoxon signed-rank test within a treatment:

```
proc univariate data = indata;
  var CHG_CCT;
  by treatment;
run;
```

#### Two-sample t-test for comparison between treatments:

```
proc ttest data = indata;
  class treatment;
  var CHG_CCT;
```

```
run;
```

Wilcoxon rank sum test for comparison between treatments:

```
proc npar1way data = indata wilcoxon;
  class treatment;
  var CHG_CCT;
run;
```

ANCOVA model for modeling the treatment effect:

```
proc mixed data = indata;
  class treatment;
  model CHG_CCT = treatment baseline_CCT;
  lsmeans treatment / cl pdiff;
run;
```

The primary analysis will use the mITT population with available data per subject at eye level (ie, ODO). Robustness analyses (details provided in Section 8.2.1) will also be presented based on the MI methodology under different assumptions of missingness and intercurrent events (where missing data or withdrawal due to lack of efficacy or AEs will be imputed using FCS regression method and missing data for all other reasons will be imputed using worst within subject observation prior to the intercurrent event).

Missing data handling using MI under different assumptions of missingness and intercurrent events are described in steps along with example SAS® code for the primary analyses one-sample t-test and two-sample t-test.

Step 1: Imputation step

The following SAS® code will be employed to produce twenty “complete” (imputed) datasets using MI FCS methodology:

```
proc mi data = indata (where (seye = eye)) seed = 999 out = outdata1
nimpude = 20;
  class treatment;
  var treatment baseline_CCT aval2 aval4 aval8;
  fcs;
run;
```

where

- `indata` is the name of the input dataset
- `outdata1` is the name of the output dataset;
- `treatment` is the treatment group variable;
- `baseline_CCT` is the baseline mean CCT value; and
- `aval2`, `aval4`, and `aval8` are the mean CCT values at Week 2, Week 4, and Week 8, respectively.

Step 2. Finalization of imputed datasets from MI under different assumptions of missingness and intercurrent events

After obtaining twenty “complete” datasets, for subjects with withdrawal due to lack of efficacy or AEs, the imputed missing values in each dataset will be replaced by the worst within subject observation from post-baseline visits (including both scheduled and unscheduled visits) prior to the intercurrent event. After replacement, change from baseline mean CCT (CHG\_CCT) will be calculated all post-baseline visits in each dataset.

### Step 3. Analysis step

For each of the “complete” datasets from step 2, the following SAS® code will be employed to run the primary analyses.

#### One-sample t-test

```
proc sort data = outdata1;
  by visit treatment _imputation_;
run;
ods output statistics = outdata2;
proc ttest data = outdata1 alpha = 0.05;
  by visit treatment _imputation_;
  var chg_cct;
run;
```

#### Two-sample t-test

```
<data outdata1;
  set outdata1;
  if treatment = "Netarsudil QD" then treatment1 = "1";
  else treatment1 = "2";
  treatment = treatment1;
  drop treatment1;
run;>
proc sort data = outdata1;
  by visit _imputation_;
run;
ods output statistics = outdata2;
proc ttest data = outdata1 alpha = 0.05;
  by visit _imputation_;
  class treatment;
  var chg_cct;
run;
```

### Step 4. Pooling step

SAS® procedure MIANALYZE will then be used to combine results from step 3 across imputations to obtain final estimates for inference.

#### One-sample t-test

```
ods output ParameterEstimates = outdata3;
proc mianalyze data = outdata2;
  by visit treatment;
  modeleffects mean;
  stderr stderr;
run;
```

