9.3 Determination of Sample Size

This study is not powered to detect a pre-stated efficacy signal, but rather will be used to inform the design and power for any possible future studies. With a sample size of up-to 20 subjects per treatment group, the precision of the point estimate of mean change from baseline in CCT, as measured by the half-width of the two-sided 90% confidence interval (CI), will be approximately 1/2.7 of the standard deviation (SD) of the change from baseline, yielding 90% confidence that the true mean change from baseline is within \pm SD/2.7 μ m of the observed mean change from baseline. That is, if the SD of the change from baseline is 60 μ m, then the half-width of the two-sided 90% CI would be $60 \mu\text{m} \times 1/2.7 = 22.2 \mu\text{m}$, yielding 90% confidence that the true mean change from baseline is within $\pm 22.2 \mu\text{m}$ of the observed mean change from baseline.

With a sample size of up-to 20 subjects within a treatment group, the study will have 80% power to reject H_{01} or H_{02} and in favor of H_{11} or H_{12} respectively and demonstrate a statistically significant mean change from baseline, assuming the true effect size (mean change / SD) is 0.577 or larger (e.g., assuming the true mean change from baseline is 34.6 μ m and the standard deviation is 60 μ m), a one sample t-test and a two-sided alpha = 0.10.

With a sample size of up-to 20 subjects per treatment group, the study will have 95% confidence of ruling out AEs with true incidence rates of 13.9% or higher within each treatment group. That is, with up-to 20 subjects in a treatment group, if an AE of a specific type is not observed, then with 95% confidence, the true incidence rate of that adverse event is less than 13.9%.

Similarly, with a sample size of up-to 40 subjects combined over treatment groups, the study will have 95% confidence of ruling out AEs with true incidence rates of 7.2% or higher within each treatment group. That is, with up-to 40 subjects in a treatment group, if an AE of a specific type is not observed, then with 95% confidence, the true incidence rate of that adverse event is less than 7.2%.

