## 4. Study Treatments

### 4.1 Treatment Administered

Subjects will be randomized using a 1:1 allocation ratio to one of two treatment groups:

- Netarsudil QD Dosing Regimen
  - Study Artificial Tear: one drop in the study eye in the morning
  - Netarsudil 0.02% ophthalmic solution: one drop in the study eye in the evening
- Netarsudil BID Dosing Regimen
  - Netarsudil 0.02% ophthalmic solution: one drop in the study eye in the morning and in the evening

Doses will be self-administered by the study subjects. If the subject is using any another topical ophthalmic drop (e.g., ocular hypotensive medications) at the same time as netarsudil, the subject should be instructed to instill netarsudil first, and wait at least 15 minutes before instilling any additional drops.

For subjects deemed unable to self-administer the doses, a caregiver will be asked to administer the medication. All subjects will administer study medication for approximately 8 weeks.

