## 5. Sample Size and Power Considerations

This study is not powered to detect a pre-stated efficacy signal, but rather will be used to inform the design and power for any possible future studies. With a sample size of up-to 20 subjects per treatment group, the precision of the point estimate of mean change from baseline in CCT, as measured by the half-width of the two-sided 90% confidence interval (CI), will be approximately  $1/2.7$  of the standard deviation (SD) of the change from baseline, yielding 90% confidence that the true mean change from baseline is within  $\pm SD/2.7 \mu\text{m}$  of the observed mean change from baseline. That is, if the SD of the change from baseline is  $60 \mu\text{m}$ , then the half-width of the two-sided 90% CI would be  $60 \mu\text{m} \times 1/2.7 = 22.2 \mu\text{m}$ , yielding 90% confidence that the true mean change from baseline is within  $\pm 22.2 \mu\text{m}$  of the observed mean change from baseline.

With a sample size of up-to 20 subjects within a treatment group, the study will have 80% power to reject  $H_{01}$  or  $H_{02}$  and in favor of  $H_{11}$  or  $H_{12}$  respectively and demonstrate a statistically significant mean change from baseline, assuming the true effect size (mean change / SD) is 0.577 or larger (e.g. assuming the true mean change from baseline is  $34.6 \mu\text{m}$  and the SD is  $60 \mu\text{m}$ ), a one sample t-test and a two-sided alpha = 0.10.

With a sample size of up-to 20 subjects per treatment group, the study will have 95% confidence of ruling out AEs with true incidence rates of 13.9% or higher within each treatment group. That is, with up-to 20 subjects in a treatment group, if an AE of a specific type is not observed, then with 95% confidence, the true incidence rate of that adverse event is less than 13.9%.

Similarly, with a sample size of up-to 40 subjects combined over treatment groups, the study will have 95% confidence of ruling out AEs with true incidence rates of 7.2% or higher within each treatment group. That is, with up-to 40 subjects in a treatment group, if an AE of a specific type is not observed, then with 95% confidence, the true incidence rate of that AE is less than 7.2%.

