#### ANCOVA model

```

<data outdata11;
  set outdata1;
  if treatment = "Netarsudil QD" then treatment1 = "1";
  else treatment1 = "2";
  treatment = treatment1;
  drop treatment1;
run;>
proc sort data = outdata11;
  by visit _imputation_;
run;
ods output lsmeans = lsm diffs = diff;
proc mixed data = outdata11;
  by visit _imputation_;
  class treatment;
  model CHG_CCT = treatment baseline_CCT / solution ;
  lsmeans treatment / pdiff cl alpha = 0.05;
  lsmeans treatment / pdiff cl alpha = 0.1;
run;

proc sort data = lsm;
  by visit treatment alpha;
run;
ods output ParameterEstimates = outdata2;
proc mianalyze data = lsm;
  by visit treatment alpha;
  modeleffects estimate;
  stderr stderr;
run;

proc sort data = diff;
  by visit treatment alpha;
run;
ods output ParameterEstimates = outdata3;
proc mianalyze data = diff;
  by visit treatment alpha;
  modeleffects estimate;
  stderr stderr;
run;

```

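### Multiple-imputation results are pooled without complete-data degrees of freedom, so the within-arm MI intervals are about 5–8% (90%) and 6–10% (95%) too narrow

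*SAP*

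**What the plan says.** SAP 12.2 creates twenty imputed datasets (Step 1) and runs the t-tests in each (Step 3). Step 4 says that the SAS "procedure MIANALYZE will then be used to combine results from step 3 across imputations to obtain final estimates for inference".

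The one-sample call opens "proc mianalyze data = outdata2". It runs by visit and treatment and receives only a mean and a standard error. The two-sample call has the same form, run by visit and class. The ANCOVA code pools the least squares means with "proc mianalyze data = lsm" and the differences in a parallel call. None of these calls has EDF=, and neither document says elsewhere which degrees of freedom apply to the MI results.

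On sample size, SAP 5 states: "With a sample size of up-to 20 subjects within a treatment group, the study will have 80% power to reject" either null hypothesis, "assuming the true effect size (mean change / SD) is 0.577 or larger", with "a one sample t-test and a two-sided alpha = 0.10".

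The primary analysis is the mITT population on observed data, using PROC TTEST. SAP 8.2.2 and 12.2 list MI as a robustness analysis next to LOCF and the per-protocol population. SAP 18 assigns it to Table 14.2.1.2.

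**The concern.** Without EDF=, the pooling step takes its degrees of freedom only from the number of imputations and the relative size of the between-imputation variance. That formula treats the complete-data sample as large. Each imputed dataset gives a t-test on 19 degrees of freedom, but that limit is lost once only the mean and standard error are passed on. The pooled test is then close to a z-test on 20 subjects.

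Table 14.2.1.2 will be read beside Table 14.2.1.1, the primary result, which uses the correct t distribution. If the two tables use different reference distributions, the MI table can show a smaller p-value and a tighter interval for a reason unrelated to how missing data were handled. A reader would credit the imputation.

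**Working it through.** **Inputs.** Up to 20 per arm, effect size 0.577 and two-sided alpha 0.10 (SAP 5); SD of change 60 µm (Protocol 9.3); 1:1 allocation (SAP 4.1); m = 20 (SAP 12.2, Step 1). Neither document gives a dropout rate, so the fraction of missing information (FMI) is an assumption, taken from 1% to 30%.

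**1. The plan's own figure.** The noncentrality is 0.577 × √20 = 2.58. With 19 df the power is 80.01%, which matches the stated 80%. A normal approximation gives 82.5%. The planning of the within-arm test therefore already relies on 19 df.

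**2. Limit of no missing data (exact).** The between-imputation variance is zero and the coded test uses the normal quantile.
- Size at nominal 0.10: 2·P(T19 > 1.645) = 11.6%. At nominal 0.05: 2·P(T19 > 1.96) = 6.5%.
- Interval shortfall: 1 − 1.645/1.729 = 4.9% (90%) and 1 − 1.960/2.093 = 6.4% (95%).
- At SD 60, the 90% half-width is 22.1 µm with the normal quantile and 23.2 µm with t on 19 df.

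**3. With missing data.** As coded, df = (m − 1)(1 + 1/r)², where r is the relative increase in variance from missing data. This equals 19/FMI². With EDF= the small-sample df is 1/(1/df_coded + 1/v_obs), where v_obs = (1 − FMI)·v0(v0 + 1)/(v0 + 3) and v0 is the complete-data df.

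Example, one-sample, FMI 5%: 19/0.05² = 7,600; v_obs = 0.95 × 19 × 20/22 = 16.4; adjusted df 16.4.

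| Analysis (v0) | FMI | df coded | df with EDF= | 90% critical value, coded / adjusted | 90% CI short by | 95% CI short by |
|---|---|---|---|---|---|---|
| One-sample (19) | 1% | 190,000 | 17.1 | 1.645 / 1.739 | 5.4% | 7.1% |
| One-sample (19) | 5% | 7,600 | 16.4 | 1.645 / 1.743 | 5.6% | 7.4% |
| One-sample (19) | 20% | 475 | 13.4 | 1.648 / 1.767 | 6.7% | 8.8% |
| One-sample (19) | 30% | 211 | 11.4 | 1.652 / 1.790 | 7.7% | 10.0% |
| Two-sample (38) | 5% | 7,600 | 34.2 | 1.645 / 1.691 | 2.7% | 3.5% |
| Two-sample (38) | 20% | 475 | 27.3 | 1.648 / 1.703 | 3.2% | 4.2% |
| ANCOVA (37) | 5% | 7,600 | 33.2 | 1.645 / 1.692 | 2.8% | 3.6% |
| ANCOVA (37) | 20% | 475 | 26.5 | 1.648 / 1.704 | 3.3% | 4.3% |

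At FMI 5% in the one-sample case, t = 1.70 gives p = 0.0892 as coded and 0.1080 with EDF = 19. These lie on opposite sides of the 0.10 level in SAP 8.4.

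**4. Simulated size at nominal 0.10** (20 per arm, m = 20, Bayesian regression imputation, data missing completely at random). In 10,000 trials per setting with correlation 0.6 between visits (Monte Carlo SE about 0.3 points), the one-sample test gave:

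| Missing | As coded | With EDF= |
|---|---|---|
| 5% | 11.0% | 9.4% |
| 10% | 11.2% | 9.4% |
| 15% | 11.3% | 9.1% |
| 20% | 11.0% | 8.9% |
| 25% | 10.6% | 8.3% |

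A separate set of 3,000 trials per setting gave 10.5–12.2% as coded and 8.4–10.3% with EDF=. The two-sample test gave 9.6–10.9% as coded in the larger set and 10.3–11.6% in the smaller.

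**5. MI interval against primary interval.** This null simulation used 6,000 trials per setting, with assumed baseline SD 50, Week 2 to Week 4 correlation 0.6 and Week 2 complete. With one, two and four values missing per arm, the MI 90% interval was narrower than the primary one in 95%, 90% and 81% of trials as coded, against 52%, 53% and 54% with EDF=. MI was significant while the primary test was not in 2.3%, 2.6% and 3.1% of trials as coded, against 1.0%, 1.4% and 1.8%.

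**The case against.** **The table is secondary, and the trial is exploratory.** This stands. A reader might infer that the primary conclusion is at risk, but the primary test runs on observed data with the correct df. A reader might also take MI to be the main robustness check; the documents list MI, LOCF and per protocol without ranking them, and Table 14.2.1.2 is not among the topline tables.

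**The effect is small, and the correction overshoots.** Largely right. The excess is about 1 to 2 points of size and about 1.1 µm of half-width (23.2 − 22.1). From about 15–20% missing, the corrected test is roughly as far below 10% as the coded one is above it, and at 25% it is further off. It would also be tempting to say that low missingness, where the correction helps most, is what this trial will see. The documents give no dropout rate to support that.

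**The two-sample and ANCOVA cases are weak.** This stands too. Their shortfall is about half and their size is near nominal, so a blanket statement about all MI intervals would blur two different magnitudes.

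**The simulations are not the full SAP procedure.** They omit Step 2, which overwrites imputed values with the worst observed value after withdrawal for lack of efficacy or adverse events. The simulated sizes are therefore approximate. The table in step 3 of the working does not depend on that choice: it needs only the FMI, and fixed replacement values add no between-imputation variance that would bring the df down.

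**The code is labelled as an example.** That does not answer the point, because no other text gives a df rule.

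**Conclusion.** The concern holds, at modest size. The within-arm MI intervals are about 5–8% too narrow at 90% and 6–10% at 95%, over FMI from near zero to 30%, and the nominal 0.10 test has a size of about 11–12%. The two-sample and ANCOVA 90% intervals are about 3% too narrow with size close to nominal. Only the MI robustness results are affected.

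The zero-missing figures are exact for 20 per arm. The others measure the gap to the small-sample adjusted interval. Because that adjustment is itself mildly conservative as missingness grows, the upper ends overstate the gap to an exact interval. The simulations rest on assumed correlations and missingness completely at random. The 90% figures assume that the same df are used for the 90% intervals, since the pooling calls set no ALPHA=.

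The Wilcoxon pooling is outside this point: it combines rank statistics, for which a complete-data df is less clearly defined.

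**What to change.** Add EDF= to the t-test and ANCOVA pooling calls in SAP 12.2, and state the rule in the text. Set the value from the actual number of mITT subjects in each imputed analysis:

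- One-sample t-test: n − 1 for the arm. The call runs by treatment, so run it separately by arm if the sizes differ.
- Two-sample t-test: n1 + n2 − 2, for the equal-variance difference row only. The call runs by class and may also return per-arm rows, to which this value does not apply.
- ANCOVA: n1 + n2 − 3.

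At full, equal enrolment these are 19, 38 and 37. They should not be fixed in advance, because the plan says only up to 20 per arm.

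No new data or imputations are needed and the primary result does not change. The cost is slightly wider MI intervals, and a mildly conservative test (size about 8–9% at nominal 10%) when missingness is around 20% or more.

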#### Two-sample t-test

```

proc sort data = outdata2;
  by visit class;
run;
ods output ParameterEstimates = outdata3;
proc mianalyze data = outdata2;
  by visit class;
  modeleffects mean;
  stderr stderr;
run;

```

Additional example SAS® code to be employed in MI step 3 and 4 for other sensitivity analyses for the primary efficacy endpoints.

#### ANCOVA model

```

<data outdata11;
  set outdata1;
  if treatment = "Netarsudil QD" then treatment1 = "1";
  else treatment1 = "2";
  treatment = treatment1;
  drop treatment1;
run;>
proc sort data = outdata11;
  by visit _imputation_;
run;
ods output lsmeans = lsm diffs = diff;
proc mixed data = outdata11;
  by visit _imputation_;
  class treatment;
  model CHG_CCT = treatment baseline_CCT / solution ;
  lsmeans treatment / pdiff cl alpha = 0.05;
  lsmeans treatment / pdiff cl alpha = 0.1;
run;

proc sort data = lsm;
  by visit treatment alpha;
run;
ods output ParameterEstimates = outdata2;
proc mianalyze data = lsm;
  by visit treatment alpha;
  modeleffects estimate;
  stderr stderr;
run;

proc sort data = diff;
  by visit treatment alpha;
run;
ods output ParameterEstimates = outdata3;
proc mianalyze data = diff;
  by visit treatment alpha;
  modeleffects estimate;
  stderr stderr;
run;

```

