### 8.4 Data Analysis Conventions

All data analysis will be performed by SDC. Statistical programming and analyses will be performed using SAS® Version 9.4 or higher. Output will be provided in rich text format (RTF) for tables and portable document format (PDF) for tables, and listings using landscape orientation. Unless otherwise specified, all study data for randomized subjects will be listed by treatment group, subject number, visit, and parameter as applicable. Only a disposition listing will be created for screen failure subjects. Summaries will be presented by treatment group and visit as applicable.

Continuous study assessments will be summarized by treatment group and visit as applicable using descriptive statistics (n, mean, median, SD, minimum, and maximum). Minima and maxima will be reported with the same precision as the raw values; means and medians will be presented to one additional decimal place than reported in the raw values. Standard deviations will be presented to two additional decimal places than reported in the raw values. Categorical study assessments will be summarized by treatment group and visit as applicable using discrete descriptive statistics (frequency counts and percentages). All percentages will be rounded to one decimal place (ie, XX.X%). Change from baseline will be calculated as follow-up visit – baseline visit.

Hypothesis testing, unless otherwise indicated, will be performed at a 2-sided with a significant level of 0.10 ( $\alpha = 0.1$ ). Where applicable, 2-sided 90% and 95% confidence intervals (CIs) will be reported. All p-values will be displayed to four decimal places, with p-values less than 0.0001 presented as "<0.0001" and p-values greater than 0.9999 presented as ">0.9999". All odds ratios less than 0.01 will be presented as "<0.01" and all odds ratio greater than 999.99 will be presented as ">999.99". Difference between netarsudil QD and netarsudil BID will be calculated as netarsudil QD – netarsudil BID.

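### In the multiple-imputation ANCOVA code (SAP 12.2), the pooled interval filed under alpha = 0.1 is the 95% interval, because PROC MIANALYZE is never given an ALPHA= value

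*SAP*

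**What the plan says.** SAP 8.4 (Data Analysis Conventions) sets the test level: "Hypothesis testing, unless otherwise indicated, will be performed at a 2-sided with a significant level of 0.10". It also sets the interval levels: "Where applicable, 2-sided 90% and 95% confidence intervals (CIs) will be reported". SAP 12.2 (Primary Efficacy Analysis) repeats the promise for the model at issue: "2-sided 90% and 95% CIs around the change from baseline within each treatment group will be presented from the ANCOVA model". It asks for both levels for the LS mean difference and for the one-sample and two-sample t-tests as well.

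The multiple-imputation code under the heading ANCOVA model in SAP 12.2 does the following:

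- PROC MIXED is run by visit and imputation with two LSMEANS statements, one at alpha = 0.05 and one reading "lsmeans treatment / pdiff cl alpha = 0.1".
- The LS means and differences are sorted and pooled with "by visit treatment alpha".
- The pooling calls are "proc mianalyze data = lsm" and "proc mianalyze data = diff". Neither has an ALPHA= option. Each reads only the estimate and its standard error.

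The SAP presents this block as example code, to be employed in steps 3 and 4 of the imputation procedure.

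**The concern.** Carrying alpha through the sort and the BY list serves only to obtain intervals at two levels, so the intent is clear. The code does not deliver it: alpha arrives at the pooling step as a label, not as an instruction.

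A programmer who follows the block gets two rows per estimate, tagged 0.05 and 0.1, with no error message. The row tagged 0.1 would be reported as the 90% interval. Because testing is at two-sided 0.10, the 90% interval is the one that should agree with the test. With the wrong limits, an ANCOVA result with a p-value between 0.05 and 0.10 would be significant at the plan's level while its interval labelled 90% included zero.

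**Working it through.** **The plan's own precision figure.** SAP Section 5 gives a 90% half-width of 22.2 µm for n = 20 per group and SD 60 µm. With the normal quantile, 1.645 × 60/√20 = 1.645 × 13.42 = 22.07 µm, or SD/2.72. The stated value follows from rounding 2.72 to 2.7, so it reproduces.

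**What reaches the pooling step.** For imputation i, PROC MIXED yields an estimate Qᵢ and a standard error Sᵢ. The LSMEANS alpha changes only the per-imputation limits, which are not pooled. The group with alpha = 0.05 and the group with alpha = 0.1 therefore hold the same 20 pairs (Qᵢ, Sᵢ).

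**What pooling does with them.** With m = 20, Rubin's rules give

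- pooled estimate Q = mean of Qᵢ
- W = mean of Sᵢ², B = variance of Qᵢ, T = W + (1 + 1/m)B
- r = (1 + 1/m)B/W and df = (m − 1)(1 + 1/r)²
- limits Q ± t(1 − a/2, df) × √T, where a is the level set on PROC MIANALYZE

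Q, T and df are identical in the two groups, and a is the same unset default in both. The limits must therefore coincide whatever the default is, and at most one of the two labels can be right. With the default at 0.05, the wrong label is 0.1.

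**Illustration on simulated data** (20 subjects per arm, four values missing, 20 imputations; Q = −47.83, √T = 10.19, df about 3,159):

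| BY group | As coded | With ALPHA= passed |
|---|---|---|
| alpha = 0.05 | (−67.80, −27.85) | (−67.80, −27.85) |
| alpha = 0.1 | (−67.80, −27.85) | (−64.59, −31.07) |

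The widths are 39.95 and 33.52, a ratio of 1.19.

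**Size in general.** The excess width is t(0.975, df)/t(0.95, df): 1.192 at infinite df, 1.201 at 37 df and 1.210 at 19 df. As coded, df = 19(1 + 1/r)² always exceeds 19, so 1.210 is a bound that is not reached. For df to fall to 37, (1 + 1/r)² would have to be 37/19 = 1.947, giving r = 2.53: a between-imputation component two and a half times the within-imputation variance. The realistic excess is about 19-20%.

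**Where label and p-value would disagree.** The documents give no standard error for a pooled LS mean. Assuming 60/√20 = 13.42 µm and large df, the 90% half-width is 22.1 µm and the 95% half-width 1.960 × 13.42 = 26.3 µm. A pooled change between 22.1 and 26.3 µm would then have p < 0.10 and an interval labelled 90% that covers zero.

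**The other calls in SAP 12.2.** The observed-data t-test and ANCOVA calls set no alpha. The t-tests on imputed data use "proc ttest data = outdata1 alpha = 0.05", which does not affect pooling, and their PROC MIANALYZE calls set no alpha. None of these tags any output as 90%.

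**The case against.** The strongest reply is that the plan itself is right. SAP 8.4 and the text of 12.2 require both interval levels, the code is called example code, and it plainly needs tidying before it will run (one option name is misspelt). A programmer working to the text must still produce a true 90% interval, and two identical rows might be noticed in checking. The affected output is also peripheral: ANCOVA is a sensitivity model, and multiple imputation is a robustness run of it. All of this stands and limits the point. It does not remove it, because the SAP says that this code is to be employed, and followed as written it mislabels an interval.

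Three stronger readings are tempting and are not supported:

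- A reader might infer that the primary analysis carries a wrong 90% interval, or that no 90% interval is planned. The observed-data and pooled t-test calls only omit a 90% run that the text requires.
- A reader might infer that testing is really at 0.05, so that power at effect size 0.577 and n = 20 is 68.7% instead of the stated 80% (80.0% on recalculation). That power statement concerns the one-sample t-test. The p-values do not depend on ALPHA=, and no decision rule in the documents uses the mislabelled interval.
- A reader might take 21% as the size. That is the value at 19 df, which the pooled degrees of freedom always exceed.

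**Conclusion.** The point holds for the multiple-imputation ANCOVA block of SAP 12.2. The LS-mean and difference intervals filed under alpha = 0.1 are 95% intervals, about 19-20% wider than the promised 90% intervals. The effect is on the ANCOVA rows of Table 14.2.1.2. Estimates, standard errors and p-values are unaffected, and the error is conservative.

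The conclusion assumes the SAS default of ALPHA=0.05 in PROC MIANALYZE, which the documents do not state. That the two labelled rows are identical does not depend on this default. This is an error in the code, not in the stated analysis.

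**What to change.** In the multiple-imputation ANCOVA block:

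1. Keep a single LSMEANS statement in PROC MIXED, or filter the LS-mean and difference data sets to one alpha value, so that each BY group has exactly 20 rows.
2. Remove alpha from the SORT and BY lists.
3. Run each PROC MIANALYZE twice, once with ALPHA=0.05 and once with ALPHA=0.10.

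Step 1 must not be skipped. If alpha is dropped from the BY lists while both LSMEANS statements remain, PROC MIANALYZE reads each result twice, 40 rows instead of 20. The between-imputation term falls from 1.05B to (38/39) × 1.025 × B = 0.999B, and the degrees-of-freedom multiplier rises from 19 to 39. That would change standard errors and p-values in the anti-conservative direction, which the present code does not do.

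For consistency with the text of SAP 12.2, also add an ALPHA=0.10 run to the pooled t-tests and to the observed-data TTEST and LSMEANS calls.

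The cost is a few lines of SAP code. Data, design and estimand do not change.
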